## 7.2.5 Sponsor Responsibility for Reporting Adverse Events

All Adverse Events will be reported to regulatory authorities, IRB/IECs and investigators in accordance with all applicable global laws and regulations.

## 8.0 STATISTICAL ANALYSIS PLAN

Sample size justification. To address the primary objective, we have calculated the 95% confidence intervals (CI's) to assess precision of expected response rate of pembrolizumab in treating patients with specified mutant tumors (e.g., *POLE*, *POLD1*, and *BRCA1* and 2). Responses to single agent PD-1 inhibition are not seen in the majority of patients; available published data in pretreated triple negative breast, lung, ovarian tumors, histologies likely to be enrolled to this trial, have ranged from 11-19% in small studies. Based on the data in MSI high tumors by Le et al, responses can be expected to rise significantly in tumors with genomic instability, with the lowest rate of 40% in their published series. We thus assume that the response rate of pembrolizumab in our trial, treating patients with *POLE* (or *POLD1*) and/or *BRCA1/2* mutant tumors, will similarly be at about 40%. For n=23 patients for each type of tumors ([*POLE* or *POLD1*] and [*BRCA1* and 2]), we expect to yield a 95% CI of (0.20, 0.60), within the 40%+/- 20% range (Table 7). This confidence interval is above the response rate of using standard therapy in treating unselected cancer patients suggesting significant improvement of pembrolizumab over standard therapies.

To address the secondary objective, we used the same 95% CI calculations (Table 7), assuming no loss of follow-up, to assess the precision of expected PFS rate of pembrolizumab at 6 months in treating patients with specified mutant. Based on the data in Le et al (Panel C Fig 2), the PFS rate at 6 months was at least 35% while the immune-related PFS at 20 weeks was at least 67%. Assuming the 6-month PFS rates in our study will be similarly at least 35%. With n=23 patients for each type of tumors ([*POLE* or *POLD1*] and [*BRCA1* and 2]), we expect to yield a 95% CI of (0.15,0.55) for PSF of 35% and (0.46,0.84) for PSF of 65%, both within the +/- 20% range.

**Table 7. 95% Confidence Intervals for Response and/or PFS\* Rate Based on Estimated Rate (P) and Sample Size (n) for a Specific Mutant Tumor.**

P							
n	0.25	0.30	0.35	0.40	0.50	0.65	0.75
20	(0.06,0.44)	(0.10,0.50)	(0.14,0.56)	(0.18,0.62)	(0.28,0.72)	(0.44,0.86)	(0.56,0.94)
23	(0.07,0.43)	(0.11,0.49)	(0.15,0.55)	(0.20,0.60)	(0.29,0.71)	(0.46,0.84 )	(0.57,0.93)
25	(0.08,0.42)	(0.12,0.48)	(0.16,0.54)	(0.20,0.60)	(0.30,0.70)	(0.46,0.82 )	(0.58,0.92)
26	(0.08,0.42)	(0.12,0.48)	(0.16,0.54)	(0.21,0.59)	(0.30,0.70)	(0.48,0.82 )	(0.59,0.91)

28	(0.09,0.4)	(0.13,0.47)	(0.17,0.53)	(0.21,0.59)	(0.31,0.69)	(0.47,0.83 )	(0.59,0.91)
30	(0.10,0.40)	(0.13,0.47)	(0.18,0.52)	(0.22,0.58)	(0.32,0.68)	(0.48,0.82 )	(0.60,0.90)
*CI calculations for PFS assumed no loss of follow-up.							

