## 1.0 TRIAL SUMMARY

Abbreviated Title	Basket Trial of Pembrolizumab
Trial Phase	II
Clinical Indication	BRCA , POLE and POLD1 mutant tumors
Trial Type	Therapeutic
Type of control	None
Route of administration	IV
Trial Blinding	None
Treatment Groups	BRCA , POLE and POLD1 mutant tumors
Number of trial subjects	40
Estimated enrollment period	18-24 months
Estimated duration of trial	30-36 months
Duration of Participation	30-36 months

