## 2.0 TRIAL DESIGN

### 2.1 Trial Design

This will be a phase II trial that will enroll two cohorts of patients: a) Patients with advanced solid tumors with *POLE* and *POLD1* mutations whose tumors exhibit a microsatellite stable phenotype and b) Patients with advanced solid tumors with *BRCA1/2* mutations. The primary endpoint will be response rate, which we anticipate to be higher than that seen historically in unselected solid tumors. Progression free survival will also be measured.

**Patient Selection and Recruitment:** Patients referred for this trial must submit pre-treatment tumor specimens for next generation sequencing analysis to characterize the presence of *POLE*, *POLD1*, or *BRCA1/2* mutations. Enrollment will be guided by presence of tumor mutations (as opposed to tumor histology). Patients with *BRCA1/2* mutations will be identified through standard of care testing for these mutations. If Foundation One next generation sequencing panel, or other similarly validated analysis, is ordered commercially prior to the patient's referral for study this analysis will be acceptable for enrollment to this protocol. Patients with *POLE/POLD1* mutations will likely be identified through Foundation One next generation sequencing panel, or other similarly validated analysis, ordered commercially prior to the patient's referral for study. This analysis will be acceptable for enrollment to this protocol. Tumors harboring hotspot mutations in *POLE/POLD1* that result in a hypermutator phenotype are expected to be microsatellite stable (MSS). Testing for microsatellite instability will be done in all *POLE* mutant cases prior to enrollment. Tumors harboring non-hotspot *POLE* or *POLD1* mutations that show clear evidence of MSI will be excluded.

[figure not shown]
Archived tumor tissue will be retrieved for correlative analyses from each patient (20 unstained slides preferred, minimum of 15 required). If inadequate archived tissue is available, a fresh tumor biopsy must be performed.

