## 2.2

### 2.3 Trial Diagram

Arm 1 is closed

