### **Rationale for Protocol Modification**

In this modification (v.04JAN2023), we are closing Arm 1 due to low accrual and removing the limitation on enrollment of patients with breast and ovarian histologies in Arm 2. The power of the study will not be affected since the study was not powered to pick up differences in response between breast/ovarian and non breast/ovarian patients. There is no mention of breast/ovarian-to other cohort comparisons. Mutations of HRD pathway are the scientific factor of interest, not ovarian/breast cohort, so there is not statistical issue with proposed change.

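### The trial summary gives 40 subjects, the SAP's precision rests on 46, and after Arm 1 closed the SAP still claims n=23 for POLE/POLD1 and sets no target for Arm 2

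*Combined protocol and SAP*

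**What the plan says.** - **Size.** In section 1.0 (Trial Summary) the row "Number of trial subjects" reads 40. BRCA, POLE and POLD1 are still listed there as the treatment groups.
- **Cohorts.** Section 2.1: "This will be a phase II trial that will enroll two cohorts of patients", namely POLE/POLD1 and BRCA1/2.
- **Basis for the sample size.** Section 8.0: "we have calculated the 95% confidence intervals (CI's) to assess precision of expected response rate". The assumed response rate is 40% in both cohorts. "For n=23 patients for each type of tumors", the plan continues, "we expect to yield a 95% CI of (0.20, 0.60), within the 40%+/- 20% range". The same n=23 is used for 6-month PFS, giving (0.15, 0.55) at 35% and (0.46, 0.84) at 65%, with no allowance for loss to follow-up. The SAP gives no overall total.
- **Comparison.** Section 8.0 cites response rates of 11-19% in pretreated unselected tumors and describes the expected interval as lying above the rate on standard therapy.
- **Closure.** Section 2.3: "Arm 1 is closed". The Rationale for Protocol Modification in section 4.2: "we are closing Arm 1 due to low accrual". Its statistical comment deals only with lifting the limit on breast and ovarian histologies.
- **Not stated anywhere.** How the 40 divides between cohorts, how many patients Arm 1 enrolled, and what Arm 2 should now recruit. Section 5.7 (Subject Replacement Strategy) is a heading without text.

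**The concern.** The plan has no hypothesis test or power calculation, so the whole case for the sample size is the precision at n=23 per cohort. That n does not fit the stated total, and one of the two cohorts has stopped recruiting. As written, a reader cannot tell how many patients the primary response rate in the open arm will rest on. The reader is also told to expect a precision for POLE/POLD1 that a cohort closed for low accrual is unlikely to reach. These are conflicts between sections of the current text, not differences from the amendment log. What is at stake is a defined n for the primary estimate and a correct precision statement for each cohort.

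**Working it through.** **Inputs.** Total 40 (section 1.0); two cohorts (section 2.1); n=23 per cohort, response rate 0.40, PFS rates 0.35 and 0.65, cited range 11-19% (section 8.0).

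**1. Reproduce the plan's figure.** The SAP does not name its CI method. The normal-approximation (Wald) interval, p ± 1.96 × √(p(1−p)/n), reproduces it.

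- Response, p=0.40, n=23: 1.96 × √(0.24/23) = 0.200, giving 0.200 to 0.600. This matches.
- PFS, n=23: 0.155 to 0.545 at 35% and 0.455 to 0.845 at 65%. These agree with the printed intervals to within rounding.
- Inverted for a half-width of 0.20: n = 1.96² × 0.24 / 0.20² = 23.05, which explains the choice of 23.
- Other methods fit less well: Wilson at p=0.40, n=23 gives 0.228 to 0.600, and the exact interval for 9/23 gives 0.197 to 0.615.

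**2. Check the total.** 2 × 23 = 46, against 40. The gap is 6 patients, or 6/46 = 13%.

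**3. What 40 would give across two cohorts.** No split is stated, so these are illustrations only (Wald, p=0.40).

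| Split | Cohort n | 95% CI | Half-width |
|---|---|---|---|
| 20/20 | 20 | 0.185 to 0.615 | 0.215 |
| 23/17 | 17 | 0.167 to 0.633 | 0.233 |

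Table 7 itself prints (0.18, 0.62) for n=20. At n=23 the lower limit of 0.200 is one point above the 19% top of the cited range. At n=20 it is below it by the SAP's method.

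**4. What the closure does to Arm 2.** The response rows use p=0.40.

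| Arm 2 n | Response 95% CI | Half-width | PFS 35% | PFS 65% |
|---|---|---|---|---|
| 23 | 0.200 to 0.600 | 0.200 | 0.155 to 0.545 | 0.455 to 0.845 |
| 30 | 0.225 to 0.575 | 0.175 | 0.179 to 0.521 | 0.479 to 0.821 |
| 40 | 0.248 to 0.552 | 0.152 | 0.202 to 0.498 | 0.502 to 0.798 |

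If the total of 40 stands, Arm 2 can reach 23 whenever Arm 1 enrolled 40 − 23 = 17 or fewer.

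**5. What the closure does to Arm 1.** The enrolled number is not given. Assuming 2 to 10 patients, two illustrations with exact (Clopper-Pearson) intervals are 0.053 to 0.853 for 2 of 5 and 0.122 to 0.738 for 4 of 10. Either is far wider than (0.20, 0.60).

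**The case against.** The strongest reply is that this is a precision-based, uncontrolled phase II trial, so no test or error rate changes, and the arm that matters is not harmed. Much of that stands, and it limits the point in several ways.

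- **A reader might infer that the stated precision is lost in both cohorts.** The documents do not support this. Closing Arm 1 removes no one from Arm 2, which at 23 to 40 patients matches or betters the stated half-width.
- **A reader might take 20 per arm as the real design.** No section says so, and an equal split is hard to envisage once one arm has closed for low accrual. Table 7 already shows the n=20 interval. The loss is 1.5 points of half-width, and whether the interval clears 19% depends on method: the exact lower limit for 8/20 is 0.191.
- **A reader might treat 19% as a decision threshold with a required number of responders.** Section 8.0 states no null value, alpha, power or success criterion. The 19% is only the top of a cited range.
- **A reader might conclude that the POLE/POLD1 objective can no longer be met.** Section 3.1 asks for the response rate to be evaluated and carries no n. A small cohort gives a wide interval, not an unanswerable objective. Patients treated in Arm 1 still have to be reported, so naming POLE/POLD1 in sections 1.0 and 3.1 is not in itself an error.
- **A reader might suspect that pooling is intended.** Section 8.0 sets n by tumor type and Table 7 is for a specific mutant tumor. Nothing proposes pooling, so a statement against it is a safeguard.

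The reply does not remove the mismatch of 40 and 46, the n=23 claim for a closed arm, or the missing target for the open one.

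**Conclusion.** The point holds in three limited parts.

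1. **By arithmetic alone:** 40 subjects cannot supply two cohorts of 23. The shortfall is 6 of 46 (13%), so the two (0.20, 0.60) intervals cannot both be delivered within the stated size.
2. **By inference:** the n=23 response and PFS intervals for POLE/POLD1 will not hold if Arm 1 closed below 23. This rests on the stated reason of low accrual, since the enrolled number is not given.
3. **By omission:** Arm 2 has no stated target. Over the plausible range of 23 to 40, its half-width at a 40% response rate runs from 0.200 to 0.152. The defect is that its n is undefined, not that its precision is poor.

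The half-widths assume the Wald method, which the SAP does not name but which reproduces its figures.

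**What to change.** - **Sections 1.0 and 8.0:** replace 40 and the 23 per tumor type with the number enrolled in Arm 1 plus a stated Arm 2 target. The target may be 23 or the remaining places of the 40; the sponsor should choose and say which. With 23, the total exceeds 40 if Arm 1 enrolled more than 17. With the remaining places, 5 patients in Arm 1 (assumption) would leave 35 for Arm 2 and a half-width of 1.96 × √(0.24/35) = 0.162. Over an assumed 2 to 10 in Arm 1, Arm 2 would have 38 to 30 patients and a half-width of 0.156 to 0.175.
- **Section 8.0:** restate the Arm 2 response and 6-month PFS intervals at the chosen n.
- **Section 8.0:** delete the n=23 response and PFS intervals for POLE/POLD1. Report Arm 1 descriptively with an exact CI at its actual n, and state that it will not be pooled with Arm 2.

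The cost is wording in the protocol and SAP and a less favourable precision statement for Arm 1. Whether the total moves from 40 depends on the target chosen and on Arm 1's enrolment.

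### Section 8.0 names no interval method; its figures match Wald intervals, which cover about 91-92% at the planning rates, and the 20-point precision at n=23 has no margin

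*Combined protocol and SAP*

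**What the plan says.** Under the sample size justification in Section 8.0, the authors write that "we have calculated the 95% confidence intervals (CI's) to assess precision of expected response rate of pembrolizumab". There is no hypothesis test, power or decision rule, so interval width is the only basis for the sample size. "For n=23 patients for each type of tumors", and with an assumed response rate of 40%, "we expect to yield a 95% CI of (0.20, 0.60), within the 40%+/- 20% range (Table 7").

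The 6-month PFS intervals at the same n are "0.15,0.55) for PSF of 35% and (0.46,0.84) for PSF of 65%, both within the +/- 20% range". The Table 7 footnote adds that "CI calculations for PFS assumed no loss of follow-up", and the text states the same assumption.

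The section sets the response-rate interval against historical rates that "have ranged from 11-19% in small studies" and reads it as an improvement. It names no interval method for planning or for the final result, and no estimator for PFS.

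**The concern.** When the interval is the only inferential tool, its method and nominal level matter. A Wald interval is known to under-cover in samples of this size, and at low counts its lower limit can fall below zero. Because the SAP is silent on method and its planning figures are Wald-type, the final analysis could default to the same formula. The precision statement would then be too favourable, and the reported 95% interval would miss the true rate more often than 5% of the time.

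PFS raises a related question. Table 7 treats 6-month PFS as a simple proportion. Section 5.6, however, ends disease-status follow-up at non-study cancer treatment, withdrawal of consent or loss to follow-up, so some patients may be censored before 6 months.

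**Working it through.** **Inputs (Section 8.0 and Table 7).** n = 23; rates 0.40 (response), 0.35 and 0.65 (6-month PFS); 95%, taken as two-sided; historical response 11-19%.

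**1. Reproduce the plan's figures.** Wald: p ± 1.96·√(p(1−p)/n).
- p = 0.40: 1.96·√(0.24/23) = 0.2002, giving 0.1998-0.6002. Printed: 0.20-0.60.
- p = 0.35: half-width 0.195, giving 0.155-0.545. Printed: 0.15-0.55.
- p = 0.65: half-width 0.195, giving 0.455-0.845. Printed: 0.46-0.84.

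Of the 42 cells in Table 7, 39 lie within 0.01 of Wald. The counts are 6 for Clopper-Pearson, 2 for Jeffreys and 0 for Wilson. A multiplier of 2 instead of 1.96 also puts 39 cells within 0.01 and matches more of them exactly at two decimals (35 against 30). The table is therefore Wald-type, perhaps with a rounded multiplier. This is inferred from the numbers, since the plan names no method.

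**2. Coverage at n = 23.** Sum the binomial probabilities of every count whose Wald interval contains the true rate.
- 0.40: counts 6 to 13, coverage 91.1%.
- 0.35: counts 5 to 12, coverage 91.7%.
- 0.65: counts 11 to 18, coverage 91.7%.

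Coverage oscillates with the true rate: 94.6% at 0.37, 94.3% at 0.42, 86.4% at 0.15. Over 0.2-0.8 it averages 92.4%. For comparison at 0.35 and 0.40, Wilson covers 95.4% and 94.6%, and Clopper-Pearson 97.2% and 96.8%.

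**3. Low counts.** Wald lower limits: 2/23 gives −2.8%; 3/23 gives −0.7%.

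**4. The 20-point statement.** Clopper-Pearson limits are the 0.025 quantile of Beta(x, n−x+1) and the 0.975 quantile of Beta(x+1, n−x). A rate of exactly 0.40 is not attainable (0.40 × 23 = 9.2), so the nearest counts are used.

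| Count | Rate | Exact 95% CI | Wider side |
|---|---|---|---|
| 8/23 | 34.8% | 16.4%-57.3% | 57.3 − 34.8 = 22.5 |
| 9/23 | 39.1% | 19.7%-61.5% | 61.5 − 39.1 = 22.4 |
| 15/23 | 65.2% | 42.7%-83.6% | 65.2 − 42.7 = 22.5 |

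Wilson at the planning rates: half-widths are 18.2 (0.35), 18.6 (0.40) and 18.2 (0.65) points, and the farther limit lies 20.3, 20.02 and 20.3 points away.

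**5. Table 7 slips at P = 0.65.**
- n = 25 prints (0.46,0.82), which is not symmetric about 0.65; the formula gives 0.463-0.837.
- n = 26 prints (0.48,0.82), width 0.34; the formula gives 0.467-0.833. The n = 28 row prints (0.47,0.83), width 0.36, so the printed interval widens as n grows.

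**6. Effect on the comparison with 19%.** Lower limits:

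| Count | Wald | Exact | Wilson |
|---|---|---|---|
| 8/23 | 15.3% | 16.4% | 18.8% |
| 9/23 | 19.2% | 19.7% | 22.2% |

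All three methods first exceed 19% at 9/23. If the true rate is 19%, the probability of 9 or more responders is 2.0%.

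**The case against.** The strongest reply is that these are planning figures. They describe expected precision on a grid of round rates, which is ordinary practice, and the plan does not say that the final interval will be Wald. That is right, so the under-coverage belongs to the printed figures and to a final analysis only if it follows them. The silence on method is itself the gap.

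Three stronger readings are tempting, and the documents do not support them.

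- A reader might infer that any valid interval breaks the 20-point statement. The exact interval does. Wilson has near-nominal coverage at the planning rates, is narrower than Wald overall, and passes 20 points on one side by at most 0.3, which disappears at the table's two decimals.
- A reader might infer that losing two patients breaks the PFS precision. At n = 21 the Wald half-width at 35% is 20.4 points, which still rounds to the printed interval. A patient censored before 6 months also contributes to a Kaplan-Meier estimate up to censoring and is not a patient removed from n. The no-loss assumption is disclosed in both text and footnote, and the n = 20 row already shows wider intervals, (0.14,0.56) and (0.18,0.62).
- A reader might infer that under-coverage favours the drug against the 19% benchmark. Step 6 shows that it does not. At a true 40%, more of the Wald error comes from upper limits that fall too low (5.4%) than from lower limits that fall too high (3.5%).

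**Conclusion.** The point holds as one of overstated precision and an unnamed method. It does not reverse any conclusion. The printed n = 23 intervals are Wald-type and cover about 91-92% at the three planning rates; this is not a fixed property of n = 23, because coverage varies with the true rate. The 20-point claim is met only by rounding at 40%. It is exceeded by 2 to 3 points on the wider side with exact intervals and is borderline with Wilson. Two Table 7 cells at P = 0.65 are wrong, though neither is at the planned n. For PFS, the binomial formula fits only if nobody is censored before 6 months, and no estimator is named for when that fails. The documents do not say how many patients would be censored, so the size of that effect cannot be stated.

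The result rests on two-sided 95% intervals, 23 evaluable patients and the inference that Wald was used.

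**What to change.** Before the analysis, amend Section 8.0 as follows.

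- Name the interval for the response rate: Clopper-Pearson, or Wilson if near-nominal average coverage is preferred. Fixing the choice in advance matters in an open-label, single-arm trial.
- Estimate 6-month PFS by Kaplan-Meier with a log-log 95% interval, and state the censoring rules.
- Recompute Table 7 with the named method at attainable counts, which also removes the P = 0.65 slips.
- If exact intervals are chosen, restate the n = 23 precision as up to about 22-23 points on the wider side, citing 19.7%-61.5% (9/23), 16.4%-57.3% (8/23) and 42.7%-83.6% (15/23).

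The cost is SAP wording and one recomputed table. It needs no extra patients or procedures, and the stated precision becomes slightly less favourable.

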## 9.0 LABELING, PACKAGING, STORAGE AND RETURN OF CLINICAL SUPPLIES

### 9.1 Investigational Product

The investigator shall take responsibility for and shall take all steps to maintain appropriate records and ensure appropriate supply, storage, handling, distribution and usage of investigational product in accordance with the protocol and any applicable laws and regulations.

Clinical Supplies will be provided by Merck as summarized in Table 8.

**Table 8. Product Descriptions**

Product Name & Potency	Dosage Form
Pembrolizumab 50 mg	Lyophilized Powder for Injection
Pembrolizumab 100 mg/ 4mL	Solution for Injection

### 9.2 Packaging and Labeling Information

Clinical supplies will be affixed with a clinical label in accordance with regulatory requirements.

### 9.3 Clinical Supplies Disclosure

This trial is open-label; therefore, the subject, the trial site personnel, the Sponsor and/or designee are not blinded to treatment. Drug identity (name, strength) is included in the label text; random code/disclosure envelopes or lists are not provided.

### 9.4 Storage and Handling Requirements

Clinical supplies must be stored in a secure, limited-access location under the storage conditions specified on the label.

Receipt and dispensing of trial medication must be recorded by an authorized person at the trial site.

Clinical supplies may not be used for any purpose other than that stated in the protocol.

## **9.5 Returns and Reconciliation**

The investigator is responsible for keeping accurate records of the clinical supplies received from Merck or designee, the amount dispensed to and returned by the subjects and the amount remaining at the conclusion of the trial.

Upon completion or termination of the study, all unused and/or partially used investigational product will be destroyed at the site per institutional policy. It is the Investigator's responsibility to arrange for disposal of all empty containers, provided that procedures for proper disposal have been established according to applicable federal, state, local and institutional guidelines and procedures, and provided that appropriate records of disposal are kept.

